- **iv. Power**
- Sample Size: Each of the 4 sites will recruit 38 infants (total $N=152$) to retain 35 infants for a total of $N = 140$ infants in the study. The initial ($N=152$) and retained ($N=140$, $n=70$ per condition) sample sizes were chosen according to feasibility of recruitment in each site as well as considerations of time and resources needed for a 4-year study.
- Power analysis for Primary Hypotheses 1 & 2: We used a simulation-based power analysis (Muthén & Muthén, 2002; Theommes et al, 2010) to estimate the power for the randomized trial with repeated measures design as evaluated with the proposed Linear mixed modeling (LMM; Laird & Ware, 1982; Wallace & Green, 2002) utilizing FIML for attrition-based missing data. *Mplus* was used for simulations and empirical analyses. Simulations were based on detecting significance in the treatment by time interaction during the intervention phase, γ_{11} . The analysis assumed a small intraclass correlation for the slope across infants (e.g., small variance of the treatment effect of 0.05; Raudenbush & Liu, 2000), a two-tailed nominal error rate of $\alpha = .05$, an initial sample size of 152 infants at baseline, and an attrition scenario of 10% loss by the end of the 3-month intervention (based on patterns observed in previous research conducted by the collaborative team). We conducted the power analysis essentially in support of Hypothesis 1 (the short-term effect at the end of the intervention phase) based on the position that Hypothesis 2 will be supported if the initial effect is then at least sustained through the follow-up period which would be evidenced by a non-significant γ_{21} parameter (no differential change). Prior published research by [name] et al. (2010) and Heathcock et al. (2008) were used to derive effect size estimates for sitting (GMFM, $d=1.21$) and reaching (toy contacts, $d=1.32$), respectively. Pilot data from [name] & [name] and [name] were used to derive

effect size estimates for global development (Bayley III, $d=0.43$) and problem solving (IGDI, $d=1.11$), respectively.

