assessed for the full potential of information. Appropriate error-rate control is discussed in a later section. Severity of neuromotor disorder (stratification variable) and fidelity of implementation will be added as covariates, and child-level characteristics, such as gender and ethnicity, also may be included in the analysis as child-level covariates. Due to the small sample size ($J = 4$) and the convenience sampling of sites involved in the study, site will be included as a *fixed* classroom level effect rather than an additional hierarchical level or random effect. Our analytic model is presented as a piecewise LMM where Y_{it} is the outcome variable score at time t for child i , TRT_{0i} is a contrast variable denoting the intervention status for child i (i.e., 0=BAU, 1=START-Play), RX_{it} is the passage of time during the intervention phase of the study from baseline to the end of the third month, and LT_{it} is the passage of time from the end of intervention through one calendar year since entering the study. While presented here as linear effects within each study phase (RX and LT), we will also explore any potential curvilinearity as well. The second line of the equation reflects the remaining fixed covariate effects ($CTRL_{0i}$ =neuromotor disorder severity, fidelity;

COV_{0i} =child covariate [i.e., gender]; and S_{0i} =site). *The model can be expanded to consider additional covariates*

$$Y_{it} = \gamma_{00} + \gamma_{01}TRT_{0i} + \gamma_{10}RX_{it} + \gamma_{20}LT_{it} + \gamma_{11}TRT_{0i}RX_{it} + \gamma_{21}TRT_{0i}LT_{it} + \gamma_{02}CTRL_{0i} + \gamma_{03}COV_{0i} + \gamma_{04}S_{0i} + u_{0i} + u_{1i}RX_{it} + u_{2i}LT_{it} + \varepsilon_{it}$$

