such as Bayley score at baseline by adding additional parameters to this portion of the model. A random intercept (u_{0i}) and random slopes ($u_{1i}RX_{it}$ and $u_{2i}LT_{it}$) will be included to capture individual differences in outcome levels at entry into the study, and change through each phase of the study (intervention and follow-up). Finally, we will include a residual term (ε_{it}). We expect that γ_{01} , the mean difference between conditions at baseline, will not differ significantly from zero, reflecting no initial group differences and an effective randomization. This parameter also serves to statistically control for any differences at baseline (significant or otherwise) that may be observed despite the random assignment to condition. The parameter, γ_{11} , as the difference between condition slopes through the end of the intervention, is expected to be significantly greater than zero, reflecting a larger rate of change in outcomes as a result of START-Play participation; and γ_{21} as the difference between condition slopes during follow-up will either be not significantly different from zero, reflecting maintenance of the net intervention effect, or significantly greater than zero, reflecting a continued improvement in outcomes due to the START-Play intervention. Estimates of effect sizes with confidence intervals will be provided.

[figure not shown]
Control of the family-wise error rate (FWER) is necessitated by the presence of multiple outcome measures as discussed in the prior **rationale for using multiple measures of developmental skills**. We define the family of tests as containing the four primary outcomes as described in the Measures section. We will control FWER by conducting the permutation step-down procedure (Westfall & Young, 1993) within a repeated measures design (Lix & Sajobi, 2010) allowing for estimation of intervention effects while controlling for correlation between outcomes due to the common theory of change construct.

Evaluation of Primary Hypotheses 3 & 4:

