A parallel process growth modeling approach as implemented in the SEM framework will be used to simultaneously address the remaining primary research hypotheses: (3) improvements in sitting and reaching as a function of the intervention will be associated with increases in global development at the end of the project (long term effect); and (4) improvements in global development will be (at least) partially mediated by improvements in problem solving as a function of the intervention at the end of the project (long-term effect). Because the global development and problem solving constructs occur over time and are characterized as improvements (i.e. changes), we consider the mediational model as a SEM (see simplified model in Figure 1) that allows multiple simultaneous direct and indirect paths while modeling growth (Cheong, 2003). This approach will allow us to assess possible mediating effects of improvements in sitting, reaching, and problem solving through the intervention period (RX) on the relationship between intervention participation (START-Play) and improvements in global development through the one-year follow-up (LT). This model will be evaluated for the significance and directionality of included path coefficients and overall model fit. It is expected that the indirect effect of the intervention (derived by tracing solid paths $A*B$, and $A*C_1*C_2$) on child outcomes will be statistically significant and the direct effects of the intervention (dashed path D) will also remain significant, thus demonstrating partial mediation. Hypothesis 3 will be evaluated by comparing the magnitude of the $A*B$ indirect effect to the direct effect, D. Hypothesis 4 will be evaluated by comparing the magnitude of the $A*C_1*C_2$ indirect effect to the direct effect, D. Partial mediation is an appropriate hypothesis as the intervention is expected to have a substantial effect on problem solving, but there are other factors beyond problem solving, sitting and reaching that contribute to improvements in global development that are represented by the direct effect. By hypothesizing that assignment to condition (START-Play) leads to proximal changes in the mediator(s) (RX) which then lead to distal effects in the outcome (LT), we also meet the requirement of temporal precedence necessary for strong mediational inferences.

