Evaluation of Secondary Hypotheses 1 & 2: Improvements in sitting, reaching, problem-solving and global development will be moderated by (1) internal variables: the severity of neuromotor disorder, health status, entry age, cognitive status at entry; and (2) external variables:

Figure 2. Mediated Effects Model for Hyp. 3 & 4

Note: RX = intervention phase; LT = follow-up phase; START-Play = assignment to condition; A,C = direct effects of the intervention on proximal & distal outcomes, B₁ & B₂ = effect of mediator(s) on other outcomes

socioeconomic status, compliance/attendance to home visits, the home environment (HOME), and overall amount of service to the family and child. Evaluation of these variables as moderators of the effect of the intervention on change in primary outcomes (sitting, reaching, problem solving and global development) will be done by modifying the LMM model equation used in evaluation primary hypothesis 2. Two three-way interaction terms, $TRT_{0i}RX_{it}MOD_{1i}$ and $TRT_{0i}LT_{it}MOD_{1i}$, where MOD_{1i} represents an individual moderator, will be added to the model to capture the intervention by time by moderator interaction. The simple effect of the moderator, MOD_{1i} , will be included as well as relevant 2-way interactions. All continuous variables will be mean-centered prior to forming cross-product interaction terms, and all categorical variables will be dummy coded prior to forming interaction terms. Each potential moderator will first be entered individually, and later in combination, with each primary outcome tested separately.

Evaluation of Secondary Hypothesis 3: Relative to infants in the BAU group, infants in the intervention group will show greater improvements in sitting control both post-intervention and at long-term follow-up. Evaluation of this secondary hypothesis will utilize the same LMM framework presented for evaluating primary hypotheses 1 and 2, with the exception that the outcome measures will be trunk forward bending, angular displacement, and velocity of trunk.

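### As worded, the mediation model takes follow-up-phase (LT) change in global development as its outcome; this omits the intervention-phase effect and rules out the expected partial mediation if the effect is exactly maintained

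*SAP*

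**What the plan says.** **Definition of LT.** In SAP section ix (Primary Hypotheses 1 & 2), LT "is the passage of time from the end of intervention through one calendar year since entering the study". The note to Figure 2 agrees: "RX = intervention phase; LT = follow-up phase".

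**Mediation outcome.** Section ix (Primary Hypotheses 3 & 4) looks at mediator change during RX and at "improvements in global development through the one-year follow-up (LT". Its temporal-precedence argument is that assignment changes the mediators in RX, "which then lead to distal effects in the outcome (LT"). Both hypotheses in that section are worded in terms of global development at the end of the project. The SAP expects the indirect effects (A×B and A×C1×C2) to be significant and the direct path D to remain significant, and calls this partial mediation.

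**What success looks like in LT.** γ21 is the arm difference in LT slope. Section ix says it "will either be not significantly different from zero, reflecting maintenance of the net intervention effect", or that it will be significantly above zero, reflecting continued improvement. Section iv powers only the short-term effect and gives this reason: "Hypothesis 2 will be supported if the initial effect is then at least sustained through the follow-up period which would be evidenced by a non-significant" result for γ21. It reads such a result as the arms not differing in their change during follow-up.

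**Mediation power.** Section iv states 80% power at N = 152 if the standardized mediator path is at least .237, with baseline correlation .32. Paths A and D are taken from the prior-research and pilot mean differences.

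**The concern.** The hypotheses ask whether the intervention's effect on global development at project end passes through the mediators. The model as worded explains only what happens to global development after the intervention stops. If START-Play raises Bayley scores by month 3 and the gain is then held, the whole effect sits in the RX slope, which is not the stated outcome. An effective and well-maintained intervention could then give a mediation result that does not match the SAP's expected pattern, and the SAP does not say how such a result would be read.

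The power statement has a related problem. Its value for D comes from effects that section iv uses for the intervention phase, and no follow-up-phase effect is given anywhere.

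**Working it through.** **1. What the LT outcome leaves out.** Section ix measures time in months, with RX running from 0 to 3 and LT from 3 to 12. From the model equation:

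- arm difference in change, baseline to month 3 = 3γ11
- arm difference in change, month 3 to month 12 = 9γ21
- arm difference in change, baseline to month 12 = 3γ11 + 9γ21

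An LT outcome carries only 9γ21. With γ21 = 0, the month-12 difference is 3γ11, all of it outside the mediation outcome.

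**2. Consequence for the path model.** In a linear mediation model, total effect = indirect effect + D. If the total LT effect is 0, then D = −(indirect effect), and the two cannot both be positive.

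**3. The SAP's 80%.** A single-path normal approximation, with 0.9 = 1 − 10% variance shared at baseline:

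- power = Φ(β√(0.9N) / √(1 − 0.9β²) − 1.96)
- β = .237, N = 152: .237 × √136.8 = 2.772; √(1 − 0.9 × .0562) = .974; 2.772/.974 − 1.96 = 0.885; Φ = 81.2%
- N = 140: 77.9%

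This is close to the stated 80%, but it concerns the mediator path alone. It says nothing about detecting D. The full growth model cannot be rebuilt because its variances are not given.

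**4. Size under maintenance.** Take A from the SAP's problem-solving effect (d = 1.11), β = .237 and unit within-arm SD. The overall mediator SD is √(1 + 1.11²/4) = 1.144, so the unstandardized path is .237/1.144 = .207. The indirect effect is 1.11 × .207 = +0.23 SD, and D = −0.23 SD when γ21 = 0.

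**5. Simulation.** One mediator, least squares, 4,000 runs per scenario, no missing data. The indirect effect counts as significant when both component paths are positive and significant. LT effects other than zero are assumptions shown as a range; 0.43 and 0.64 are figures that section iv gives for the Bayley in the intervention phase. N = 152, β = .237:

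| Total effect on outcome (d) | True D | Indirect significant | D significant, positive | Both |
|---|---|---|---|---|
| 0 (maintenance) | −0.23 | 74% | 0.1% | 0.0% |
| 0.20 | −0.03 | 74% | 1.5% | 0.5% |
| 0.43 | +0.20 | 75% | 19% | 9% |
| 0.64 | +0.40 | 76% | 59% | 40% |
| 0.80 | +0.55 | 79% | 85% | 65% |

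At d = 0, both-significant also stays at 0.0% with β = .35 (indirect significant 97%) and with N = 140.

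**6. Calibration.** At d = 0.43 the simulation finds the total effect 75% of the time, against the 48% that section iv states for the intervention-phase slope. The simple model is therefore more precise than the SAP's, and the non-zero rows are probably optimistic.

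**The case against.** Several objections have force.

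- **Maintenance is only one success pattern.** Section ix also accepts γ21 > 0. There is then an LT effect to mediate, and the conflict does not arise in the same form. This stands.
- **Non-significant is not zero.** The SAP never asserts γ21 = 0 as a parameter value. This stands, although section iv glosses the non-significant result as no differential change.
- **A reader might infer that maintenance leaves nothing to mediate.** That goes too far. An indirect effect can exist with a zero total effect, and in the simulation it was significant in 74% of runs. What cannot exist is a positive indirect effect alongside a positive D.
- **A reader might infer that a maintained effect must fail Hypothesis 3.** The documents do not establish this. The hypothesis allows at least partial mediation, section ix evaluates it by comparing the size of the indirect effect with D, and a significant D is stated as an expectation. The numbering also differs: problem-solving mediation is Hypothesis 3 in section ii and Hypothesis 4 in section ix. The outcome is the same for both mediation hypotheses of section ix, so the point applies to each.
- **The LT-slope reading is partly an inference.** The diagram is not available to us, the text calls it simplified, and its note labels the paths differently from the text. The outcome wording could be meant cumulatively, and the four mediation steps in section viii name no phase. But section viii defines no alternative outcome, both definitions of LT confine it to follow-up, and the temporal-precedence argument depends on that split.
- **The RX/LT split was chosen for temporal precedence.** True, and any cumulative outcome weakens that argument. The fix has to concede this.

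**Conclusion.** The point holds in conditional form. As worded, the mediation outcome is follow-up-phase change, which omits 3γ11 from the month-12 effect that the hypotheses name. If the effect is exactly maintained, the total LT effect is zero and same-sign partial mediation cannot occur; an indirect effect could appear only with an opposite-sign D. If γ21 > 0, mediation of LT change remains possible, though the simplified model meets the joint expectation in only about 9% of runs at an LT effect of 0.43 and 40% at 0.64.

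Separately, the 80% mediation power uses a D drawn from effects that section iv applies to the intervention phase, so it does not describe an LT outcome.

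These conclusions rest on reading LT as the SAP defines it. The percentages also rest on a single-mediator approximation. Hypotheses 1 and 2 are unaffected, and γ11 still tests the short-term Bayley effect. Because a primary hypothesis is involved, the outcome should be settled before analysis.

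**What to change.** 1. Define the primary mediation outcome as the month-12 Bayley level adjusted for baseline, or as baseline-to-month-12 change (3 × RX slope + 9 × LT slope). Keep the LT-slope model as supplementary.
2. Limit the temporal-precedence claim. The month-12 level is measured after the month-3 mediators, but Bayley change in months 0–3 overlaps them in time.
3. Base D on the chosen outcome and restate the mediation power, saying whether it covers the mediator path alone or the indirect and direct effects together. The change aligns outcome and hypothesis but does not itself restore 80% for the joint criterion: if a maintained total effect is d = 0.43, the same simulation gives about 9%.
4. State how an indirect effect with an opposite-sign D would be interpreted, and align hypothesis numbers and path labels between the text and the figure note.

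The cost is SAP wording, a re-parameterised growth model and a new power simulation. No new data are needed: the Bayley is already scheduled at months 0, 3, 6 and 12 (SAP Table 2).

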- c. problem-solving Variable: IGDI problem-solving score
- d. global development Variable: Bayley III score

Hypothesis 2: Compared to the BAU group, the START-Play group will show greater sustained improvements from pre-intervention to one year since start of intervention (long-term effect) in:

- a. sitting Variable: Gross Motor Function Measure (GMFM) sitting scores
- b. reaching Variable: Number of toy contacts
- c. problem-solving Variable: IGDI problem-solving score
- d. global development Variable: Bayley III score

Hypothesis 3 (Mediation): Improvements in global development will be (at least) partially mediated by improvements in problem-solving as a function of the intervention at the end of the project (long-term proximal effect).

Variables: GMFM scores, toy contacts, IGDI problem-solving and Bayley III scores.

SECONDARY HYPOTHESES

Analysis of moderators

1. *Hypothesis:* Severity of motor impairment will have a significant influence on overall change in IGDI problem-solving, and motor scores, as well as Bayley III scores. Variable: Severity score (see Table 1)

2. *Hypothesis:* Factors external to the child (socialization opportunities [Modified Parent Child Interaction-Dyadic Mini Code scores (Censullo, 1991) (PCI-DMC)], and home environment (HOME Inventory [Bradley, 1993] & SES), will have a moderate effect on change in GMFM, problem-solving, and Bayley III scores.

Further analysis of motor variables

3. *Hypothesis:* The START-Play group will show posture control measures that are closer to normative values than the BAU group from pre to post intervention. This hypothesis tests additional variables quantifying sitting to supplement Primary Hypothesis 1. Variables: Kinematic measures taken from video analysis.

4. *Hypothesis:* Compared to the BAU group, the START-Play Intervention group will show greater improvements in duration of toy contact and object manipulation from pre to post intervention. This hypothesis tests additional variables quantifying reaching to supplement the

Primary Hypothesis 2. Variables: Unilateral and bilateral contact number and duration, and type of contact (i.e. hand open or closed; palmar or dorsal hand surface, manipulation variables).

iii. Research Design

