- Based on our previously stated assumptions and the cited pilot data and prior research, power analyses suggest that the targeted sample size will be sufficient to detect the reported effects with greater than 80% power for three of the four primary outcomes. With $N=152$ initial participants, power to detect mean group differences in slopes during the intervention period is >99% for sitting, 93% for reaching, and >99% for problem solving. As these three outcomes are estimated to be over-powered based on pilot/cited data, given the projected initial sample size of $N=152$ we would be able to detect effect sizes as small as $d=0.48$ for sitting, $d=0.66$ for reaching, and $d=0.56$ for problem solving. Based on the effect size derived from pilot data, power to detect mean group differences in global development improvement during the intervention period at the $d=0.43$ level is only 48%; however, given the projected sample size, we would be able to detect an effect size of $d=0.64$ with 80% power.
- *Power analysis for Primary Hypotheses 3 & 4:* Continuing to use the variability and mean differences from the cited prior research and pilot data as estimates of paths A and D in Figure 2, we conducted an empirical power analysis based on the SEM model presented in Figure 2 using an initial sample size of $N = 152$ infants, and assuming a moderate correlation between the measures at baseline ($r = .32$, explained variance = 10%). With these assumptions, we will have 80% power to be able to support the hypotheses of partial mediation of intervention-driven change over time in global development by intervention-driven changes in sitting and reaching and problem solving if the standardized parameter estimate of the mediator(s) on change in global development (paths B (Hyp. 3) or $C_1 * C_2$ (Hyp. 4) in Figure 2) is at least $\beta=.237$, which corresponds to a medium effect.

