over time between motor skill and cognitive skill. Testing for mediation will take place by 1.) showing that global development change is influenced by change in sitting and reaching and 2.) change in reaching and sitting are linked to problem solving, 3.) change in problem solving is linked to change in global development and 4.) the effect of change in sitting and reaching on global development is at least partially explained by change in problem solving.

Other factors which may be moderators of the final outcomes are 1) severity of neuromotor disorder, 2) health status, 3) age at entry, 4) cognition at entry. Factors external to the child which may moderate outcomes are: 1) Socioeconomic status, 2) compliance or attendance to the program visits, 3) the home environment (HOME), 4) overall amount of service provided to the child, and 5) fidelity of intervention implementation. We expect that these moderating variables will not be different between groups because of our randomization process, however tests for initial differences between groups will verify this. In addition, testing for moderation will take place after the primary research questions are addressed. Variables will be tested individually first and later in combination to account for increases in explained variability.

ix. Data Analysis: Evaluation of Specific Aims and Hypotheses

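### The mediation hypothesis asks for at least partial mediation, but the SAP evaluates it by a magnitude comparison and a pattern with a significant direct effect; neither matches the hypothesis or its 80% power.

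*SAP*

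**What the plan says.** SAP section ii, like section 1 of the protocol, lists as primary Hypothesis 3: "Improvements in global development will be (at least) partially mediated by improvements in problem-solving as a function of the intervention".

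SAP section ix (Evaluation of Primary Hypotheses 3 & 4) gives this hypothesis the number 4 and uses number 3 for the link from sitting and reaching to global development. It contains three statements on how the mediation model will be judged:

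- The model is assessed for the significance and direction of its path coefficients and for overall fit.
- A sentence opening "It is expected that the indirect effect of the intervention" anticipates a significant indirect effect and adds that "the direct effects of the intervention (dashed path D) will also remain significant, thus demonstrating partial mediation".
- The evaluation sentence reads "Hypothesis 3 will be evaluated by comparing the magnitude of the $A*B$ indirect effect to the direct effect, D". A parallel sentence says the same for Hypothesis 4, with A*C1*C2 in place of A*B.

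SAP section viii describes a separate four-step test. Its last step asks whether "the effect of change in sitting and reaching on global development is at least partially explained by change in problem solving". No step requires a significant direct effect.

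SAP section iv claims 80% power to support partial mediation if the standardised mediator path is at least .237.

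**The concern.** At least partial mediation is true when the indirect effect is above zero, whether or not a direct effect remains. The matching test is therefore of the indirect effect. The one explicit evaluation sentence compares two estimates instead. Their relative size does not show that either differs from zero, and no result of the comparison is tied to a conclusion.

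The pattern said to demonstrate mediation also includes a significant D. Under full mediation D is zero, so a true hypothesis would not show the pattern. The SAP is silent on the likely case of a significant indirect effect with a non-significant D. Section viii offers another route, so the rule for a primary hypothesis could be chosen after the data are seen. The 80% power would also not describe the chance of a positive conclusion if D counted.

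**Working it through.** **Inputs (SAP section iv).** 152 infants enrolled and 140 retained, 70 per arm; the 10% attrition scenario gives 152 × 0.9 = 137. Effects: IGDI 1.11 (path A) and Bayley III 0.43. Mediator path .237. Two-sided alpha .05, stated for Hypotheses 1 and 2 and assumed here for the mediation paths. For Bayley III at 0.43, the SAP says power at that "level is only 48%; however, given the projected sample size", and then names 0.64 as detectable with 80% power.

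**Model (simplified stand-in for the Mplus model).** One mediator, balanced arms T: M = 1.11·T + e, and Y = .237·M + D·T + e, with within-arm SD 1 for both. The residual SD of Y is √(1 − .237²) = 0.972. The indirect effect counts as significant when both A and B are. At least 20,000 runs per case.

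**Step 1: the plan's 80%.** For B at 140 infants, SE = 0.972/√140 = 0.082 and .237/0.082 = 2.89, so power is Φ(2.89 − 1.96) = 82%. Simulation gives 80% at 137, 81% at 140 and 84% at 152. The stated 80% is reproduced at the retained size, for the indirect effect alone and whatever the value of D.

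**Step 2: the plan's 48%.** SE = 0.64/2.80 = 0.228, and 0.43/0.228 = 1.88, so power is Φ(1.88 − 1.96) = 47%. With SD 1 the group difference would have SE 2/√140 = 0.169. The SAP's own figures thus imply a within-arm SD of about 0.228/0.169 = 1.35. Both noise levels are used below.

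**Step 3: what D might be.** Section iv uses the pilot differences as estimates of paths A and D, but does not say whether 0.43 is the direct or the total effect. If direct, D = 0.43. If total, D = 0.43 − 1.11 × .237 = 0.43 − 0.263 = 0.167. Full mediation is D = 0.

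**Step 4: the magnitude comparison.** The indirect effect is 0.263 in each case. It is smaller than D when D = 0.43 and larger when D = 0.167. The ordering flips although the mediation is the same, so it cannot say whether mediation exists.

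**Step 5: power if a positive, significant D is also required (140 infants, B = .237).**

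| Case | D | Indirect alone, SD 1 | Indirect and D, SD 1 | Indirect alone, SD 1.35 | Indirect and D, SD 1.35 |
|---|---|---|---|---|---|
| 0.43 is the direct effect | 0.43 | 81% | 46% | 54-55% | 14% |
| 0.43 is the total effect | 0.167 | 81% | 8% | 54-55% | 2% |
| Full mediation | 0 | 81% | 0.9% | 54-55% | 0.4% |
| Larger direct effect | 0.64 | 81% | 73% | 54-55% | 31% |

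With SD 1.35, a raw path of .237 is a smaller standardised path. Raising B to 0.322 (0.322/1.35 = 0.24 standardised) restores 81% for the indirect effect alone. The joint figures are then 26%, 2% and 1% for the first three cases (the total-effect D becomes 0.43 − 1.11 × 0.322 = 0.073).

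**The case against.** A reader might infer that the SAP lays down a pass/fail rule under which full mediation is rejected. The text does not go that far. The sentence on D states an expectation and labels a pattern as partial mediation. Nothing says mediation is rejected when D is not significant. Section viii does not require D, and section ix already plans to look at path significance and expects a significant indirect effect. The power statement, made through the mediator path, suggests that the planners had the indirect effect in mind.

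A reader might also infer that true partial mediation would rarely be declared. One tempting calculation takes 0.43 as the total effect and the SE of 0.228 from step 2. With a quarter of the effect mediated, D = 0.75 × 0.43 = 0.32 and 0.32/0.228 = 1.41, so power for D is 29%, falling to 5% under full mediation. The documents do not support this as a general ceiling. Section iv uses the pilot differences for path D, which favours reading 0.43 as direct. The 48% and 0.64 also belong to the intervention phase, whereas section ix places the mediated outcome in the one-year follow-up.

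Nor does the SAP say that the indirect effect must exceed D. If it did, the joint rate would be at most about 2% in every case run, but no direction is given.

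These objections limit what can be said about a fixed rule and about size. They leave in place that the only explicit evaluation sentence is not a test of mediation, and that the significant-indirect, non-significant-D result has no stated conclusion.

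**Conclusion.** The concern holds as a mismatch between hypothesis, evaluation rule and power statement. The hypothesis needs a test of the indirect effect. The SAP offers an undirected magnitude comparison, an expected pattern that excludes full mediation, and a different four-step test elsewhere.

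The 80% power stands for the indirect effect alone. If D were also required, the chance of a positive conclusion would be about 14-46% with 0.43 as the direct effect, 2-8% with it as the total effect, and under 1% under full mediation (about 1% with the rescaled mediator path). A D of 0.64 would give 31-73%. All are below 80%, so section iv's summary claim of at least .80 power for each primary hypothesis at a medium effect would not hold under that criterion.

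The figures are illustrative. They come from a single-mediator regression rather than the planned growth model. The figure is not available to confirm what D points to, and the SAP gives no precision for D in the follow-up phase. The treatment-effect tests for Hypotheses 1 and 2 are unaffected.

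**What to change.** In SAP section ix, under Evaluation of Primary Hypotheses 3 & 4:

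- State that at least partial mediation is concluded when a bootstrap or other asymmetric confidence interval for the relevant indirect effect excludes zero in the expected direction: A*C1*C2 for problem-solving, A*B for sitting and reaching.
- Remove the magnitude comparison and the significant-D pattern as criteria. Report D and the proportion mediated with intervals, as description only.

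In section iv, state that the 80% refers to the indirect effect. Bring the four steps in section viii into line with the new rule. Use one numbering for the mediation hypothesis throughout, and one set of path labels: the note to Figure 2 uses A, C, B1 and B2, while the text uses A, B, C1, C2 and D.

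The cost is SAP wording, to be settled before outcome data are examined. No new data or larger sample is needed, and the intervals are standard Mplus output.
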